9.2 Secondary Efficacy Variables

9.2.1 Time until Recovery

Time until recovery is defined as date and time of the evacuation of the first of two consecutive normal stools or no stool within 12 hours *after the first normal stool*. The time until recovery definition and SAS code can be referred to Figure 9-1. The time until recovery and additional table of time until recovery for each day of the study will be summarized using Kaplan-Meier analysis as Tables 14.2.1 using FA and PP samples. Figures for time until recovery at end of treatment can refer to Figure 14.2.1.3 and Figure 14.2.1.4, respectively.

Subgroup analysis of time until recovery by age group (< 24 months old and \geq 24 months old) will be also summarized using Kaplan-Meier analysis as Table 14.2.6 using FA and PP samples. Figures for time until recovery at the end of treatment can refer to Figure 14.2.6.3 and Figure 14.2.6.4, respectively.

Subgroup analysis of time until recovery by weight group (in infants less than 9 kg, in infants from 9 kg to < 13 kg, in children from 13 kg to 27 kg, and in children of more than 27 kg) will be also summarized using Kaplan-Meier analysis as Table 14.2.11 using FA and PP samples. Figures for time until recovery at the end of treatment can refer to Figure 14.2.11.3 and Figure 14.2.11.4, respectively.

9.2.2 Number of Subjects Recovered

Number and proportion of subjects recovered, in total and until each individual treatment day will be summarized with count and percentage as well as 95% CI as Table 14.2.2 using FA and PP samples.

Subgroup analysis of number and proportion of subjects recovered by age group (< 24 months old and \geq 24 months old) will be also summarized with count and percentage as well as 95% CI as Table 14.2.7 using FA and PP samples.

Subgroup analysis of number and proportion of subjects recovered by weight group (in infants less than 9 kg, in infants from 9 kg to < 13 kg, in children from 13 kg to 27 kg, and in children of more than 27 kg) will be also summarized with count and percentage as well as 95% CI as Table 14.2.12 using FA and PP samples.

9.2.3 Assessment of Treatment Success by the Physician

The assessment of treatment success by the physician will be done using the Global Physician Assessment.

GPA score:

- 1 =Complete relief of acute diarrhea,
- 2 = marked improvement of acute diarrhea,
- 3 = moderate improvement of acute diarrhea,
- 4 = slight improvement of acute diarrhea,
- 5 = no change in acute diarrhea,

6 = worsening of acute diarrhea.

Individual subject global physician assessment is listed in Listing 16.2.6.3. Treatment will be rated as success when the GPA score equals 1 or 2. The assessment of treatment success by the physician will be summarized with count and percentage as well as 95% CI as Table 14.2.3 using FA and PP samples.

Subgroup analysis of assessment of treatment success by age group (< 24 months old and \ge 24 months old) will be also summarized with count and percentage as well as 95% CI as Table 14.2.8 using FA and PP samples.

Subgroup analysis of assessment of treatment success by weight group (in infants less than 9 kg, in infants from 9 kg to < 13 kg, in children from 13 kg to 27 kg, and in children of more than 27 kg) will be also summarized with count and percentage as well as 95% CI as Table 14.2.13 using FA and PP samples.

9.2.4 Number of Stools and Watery Stools per Day for Toilet-Trained Subjects

Number of stools per day as well as number of watery stools per day from start of treatment and until end of study treatment will be summarized as Table 14.2.4 using FA and PP samples.

Subgroup analysis of number of stools per day as well as number of watery stools by age group (< 24 months old and \geq 24 months old) will be also summarized as Table 14.2.9 using FA and PP samples.

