4 STUDY DESIGN

4.1 Overall Study Design and Plan-Description

This is a prospective, open-label, multicenter, single-arm study evaluating the efficacy and safety of Racecadotril in infants and children with acute diarrhea in out-patients. The number of subjects to be screened is 50 in order to achieve 40 subjects treated with standard treatment (oral rehydration solution, ORS) plus Racecadotril.

1.5 mg/kg of Racecadotril will be administered, 3 times daily, via the oral route. Study drug intake will start either with the noon or evening dose on day 1.

In infants less than 9 kg: one 10 mg sachet 3 times daily.

In infants from 9 kg to <13 kg: two 10 mg sachets 3 times daily.

In children from 13 kg to 27 kg: one 30 mg sachet 3 times daily.

In children of more than 27 kg: two 30 mg sachets 3 times daily.

Standard treatment is oral rehydration solution (ORS) according to the registered local label and the instruction of the investigator. At the start of the trial, alignment will be reached on the understanding of treatment of standard ORS with the principal investigator with the aim to use the same brand of ORS for the subjects throughout the trial. ORS treatment will be documented in the CRF.

Screening and Enrolment (Day 1, Visit 1)

Subjects presenting with acute diarrhea will be evaluated for eligibility. They will undergo a physical examination including vital signs, a review of their medical history including vaccination history and concomitant medication. If the subjects are eligible, demographics, number of stools during the last 12 hours will be assessed as baseline values. On Day 1, the subject will start with study treatment. The starting dose will either be the noon, or evening dose depending on the timing of Visit 1.

Treatment period (until recovery, maximally 5 days)

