Subjects will be treated with Racecadotril three times daily according to the body weight dose requirement on an out-patient basis for maximum 5 days. The subjects will be treated with ORS (according to the registered local label and the instruction of the investigator) in addition to Racecadotril. ORS will be prescribed by the investigator and will be taken according to the product label and the instruction of the investigator. The parent(s)/caregiver(s)/legal representative(s) will be instructed to stop study drug treatment when the patient recovered. On each day, the parent(s)/caregiver(s)/legal representative(s) will fill in their diaries, documenting the date and time of each individual stool, the stool consistency of each stool (diarrheal/watery or normal), the amount of ORS, and the study drug intake. After the occurrence of two consecutive normal stools or no stool within 12 hours, the parent(s)/caregiver(s)/legal representative(s) can stop recording of the diary and return to the study site for the end of treatment visit. The date of recovery is the day when the first of two consecutive normal stools were excreted or the day

[figure not shown]
when no stool within 12 hours after the first normal stool was observed. AEs are to be reported on an ongoing basis.

End of treatment (Day 6 or early recovery, Visit 2)

The last dose of study drug will be the morning dose of day 6, if not recovered earlier (last dose will be the morning dose after recovery, ORS can be continued until Visit 2). On the same day, or within 24 hours after recovery (in exceptional cases within 48 hours), the parent(s)/caregiver(s)/legal representative(s) will visit the site for the end of treatment visit of the child. Data on vital signs, AEs, physical examination and concomitant medication will be collected. Subjects will return their diaries and unused medication.

Safety follow-up

A phone call will be performed 5-7 days after the end of the treatment period for the safety follow-up.

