10.3 Efficacy

The primary efficacy variable is the duration (hours) of diarrhea (treatment duration max 5 days). Duration of diarrhea is defined as date of the evacuation of the last watery/diarrheal stool before recovery or end of treatment.

The primary parameter, duration of diarrhea, will be analyzed using descriptive statistics. In addition, a Kaplan-Meier plot will be generated for which summary statistics will be presented as well.

The secondary efficacy variables are

- Time until recovery, defined as date and time of the evacuation of the first of two consecutive normal stools or no stool within 12 hours after the first normal stool.
- Number of subjects recovered; in total and until each individual treatment day
- Mean and median time until recovery
- Assessment of treatment success by the physician:
The assessment of treatment success by the physician will be done using the Global Physician Assessment.

GPA score:

- 1 = Complete relief of acute diarrhea,
- 2 = marked improvement of acute diarrhea,
- 3 = moderate improvement of acute diarrhea,
- 4 = slight improvement of acute diarrhea,
- 5 = no change in acute diarrhea,
- 6 = worsening of acute diarrhea.

Treatment will be rated as success when the GPA score equals 1 or 2.

- Number of stools at baseline and per treatment day for toilet-trained subjects, only.
- Number of watery stools per day for toilet-trained subjects, only.

Secondary efficacy parameters will be analyzed similarly to the primary analysis. All parameters will also be summarized using descriptive statistics.

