5.2 Time-Related Definitions

All assessment dates will be related to the first day of study drug administration. This first day of drug administration is referred to as Day 1. Day -1 is the day that is preceding Day 1 and a Day 0 will not be defined.

The baseline period will be defined as the period from informed consent to the first study drug administration. The baseline value for a variable is defined as the last non-missing value collected before the first study drug administration.

The endpoint value for efficacy variables is defined as the last non-missing value assigned to treatment for the subject. When a patient doesn't recover beyond the study cutoff date, survival duration is stopped at the study cutoff date and it will be regarded as a censored data. The cut-off date will be the end of study (treatment duration maximal 5 days).

All variables planned to be measured at one or more time points and supposed to be time-related will be windowed.

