9.2.5 Number of Stools and Watery Stools (Additional Table Requested by Abbott)

Number of stools as well as number of watery stools from start of treatment and until end of study treatment and for each day of the study will be summarized as Table 14.2.5 using FA and PP samples.

Subgroup analysis of number of stools as well as number of watery stools by age group (< 24 months old and \geq 24 months old) will be also summarized as Table 14.2.10 using FA and PP samples.

10.EXTENT OF EXPOSURE AND DRUG COMPLIANCE

The randomization (only for Protocol Version dated 09 OCT 2017) will be listed in Listing 16.2.5.1.

All study drug dispensation and retrieve to each subject will be listed in Listing 16.2.5.2. Individual subject study drug administration record will be listed in Listing 16.2.5.2. In listing 16.2.5.2, for data collection of Racecadotril dosage, a NTF (Abbott_RACE3002_NTF_Racecadotril dosage per sachet_20190321) from Abbott is adapted to extract the dosage with unit from column of "Relevant Information Related to Study Drug Dispensation".

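### Stool counts are summarised per day, but the day is not defined and Day 1 and the last day are part-days, so on a calendar-day reading frequency tends to rise falsely from Day 1 to Day 2

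*SAP*

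**What the plan says.** - **The counts.** SAP 9.2.4 (Tables 14.2.4 and 14.2.9, toilet-trained children) summarises "Number of stools per day as well as number of watery stools per day from start of treatment and until end of study treatment". SAP 9.2.5 (Tables 14.2.5 and 14.2.10, requested by the sponsor, without the toilet-trained limit) gives the same counts "until end of study treatment and for each day of the study will be summarized as Table 14.2.5". Neither section gives a time denominator.
- **The start.** Protocol 4.1: "The starting dose will either be the noon, or evening dose depending on the timing of Visit 1". A morning start is not foreseen. The diary is handed out at Visit 1 (flow charts, Protocol 8.6 and SAP 3.8).
- **The end.** Protocol 4.1: "The last dose of study drug will be the morning dose of day 6, if not recovered earlier". A child who recovers sooner takes the last dose on the morning after recovery, and Protocol 8.3 lets diary recording stop once recovery is established.
- **The day rule.** SAP 5.2: "This first day of drug administration is referred to as Day 1". The same section adds: "All variables planned to be measured at one or more time points and supposed to be time-related will be windowed". No windows follow, there or elsewhere in the SAP.
- **Counting by date elsewhere.** SAP 10.1 computes exposure as last date minus first date plus 1.
- **Baseline.** Protocol 10.3 lists "Number of stools at baseline and per treatment day for toilet-trained subjects, only". Protocol 4.1 takes the baseline stool count over the preceding 12 hours.

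**The concern.** A count per day can be compared across days only if the days are equally long. Here the first day is short for every child by design, and the last is short as well. If stools are binned by calendar date, the Day 1 mean is too low and Day 2 looks like a worsening after treatment starts, even when true frequency is steady or falling.

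The study has a single arm, so no control group shares the artefact and cancels it; the course over days is what these tables have to offer. Day 1 also mixes noon and evening starters. Its level therefore depends partly on clinic hours, and two small age subgroups could differ on Day 1 only because their mix of start times differs.

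**Working it through.** The plan states no figure for this endpoint. Its only sizing figure, a precision of 3.1 percentage points for a recovery proportion, does not enter here.

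**Assumptions, none of them from the documents.** First dose at 12:00, 18:00 or 20:00; last dose at 08:00 (range 06:00 to 10:00); 6 stools per 24 h at the start; stools spread evenly over 24 h; diary still running through the whole of Day 2.

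**Step 1: share of Day 1 observed** = (24 − start hour)/24.

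**Step 2: calendar-day counts.** Day 1 = 6 × share. Day 2 = 6 if the rate is constant, or 6 × 0.75 = 4.5 if it falls by 25%.

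| First dose | Hours on Day 1 | Share | Day 1 count | Day 2/Day 1, constant rate | Day 2/Day 1, true 25% fall |
|---|---|---|---|---|---|
| 12:00 | 12 | 50% | 3.0 | 6/3 = 2 | 4.5/3 = 1.5 |
| 18:00 | 6 | 25% | 1.5 | 6/1.5 = 4 | 4.5/1.5 = 3 |
| 20:00 | 4 | 17% | 1.0 | 6/1 = 6 | 4.5/1 = 4.5 |

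The ratios do not depend on the value 6.

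**Step 3: last day.** From midnight to 08:00 is 8/24 = 33% of a day (25% to 42% for 06:00 to 10:00). A constant rate of 6 would show as 2 on Day 6, a false fall to one third.

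**Step 4: smooth decline.** Let the rate halve every H hours, so that the count from hour a to hour b is (6/24)/k × (e^(−ka) − e^(−kb)) with k = ln 2/H. For H = 24:

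- Calendar days, noon start: 2.5, 3.1, 1.5, 0.8, 0.4, 0.1. Day 2 is 1.2 times Day 1.
- Calendar days, 20:00 start: 0.9, 3.9, 1.9, 1.0, 0.5, 0.1. Day 2 is 4.1 times Day 1.
- Consecutive 24-hour periods from first dose, any start: 4.3, 2.2, 1.1, 0.5, 0.3, a steady fall.

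Setting the Day 1 count equal to the Day 2 count and solving for H shows that the false rise disappears only if the rate halves faster than about every 17 h (noon start), 6 h (18:00) or 4 h (20:00).

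**Step 5: uneven stools.** If stools fell only between 07:00 and 21:00 (14 h), Day 1 would hold 9/14 = 64% of a day's stools for a noon start, 3/14 = 21% for 18:00 and 1/14 = 7% for 20:00. The distortion shrinks for noon starters and grows for evening starters.

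**Step 6: baseline.** At 6 per 24 h, the 12-hour baseline count is 3, beside 6 for a full day.

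**The case against.** The strongest reply is that calendar-day binning is an inference. SAP 5.2 ties dates to the first dosing day but does not say how stools are binned, and it promises windows. A maximum of five treatment days spread over six dates leaves a 24-hour reading open. That stands: the documents do not say outright that a part-day count will be reported as a daily count. It does not close the gap, because no window is written down and the one computed duration in days (SAP 10.1) goes by date, so a programmer would most likely use dates.

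Three further points stand as limits:

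- A reader might infer that stool frequency will appear to rise throughout treatment. It will not: the false rise lies between Day 1 and Day 2, and the short last day exaggerates improvement.
- A reader might treat all four tables as stated secondary efficacy variables. Only the counts in toilet-trained children are (SAP 3.6); Tables 14.2.5 and 14.2.10 were added at the sponsor's request.
- The summaries are descriptive, with no test or decision rule, and individual stool records are listed (Listing 16.2.6.2), so the counts could be rebuilt later.

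Dividing each count by the hours recorded looks like a natural remedy, but it is not neutral. Recording may stop because of two normal stools or 12 stool-free hours, so the denominator depends on the outcome; one stool in a 3-hour fragment would become 8 per 24 h.

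**Conclusion.** The point holds as an undefined day with part-days left unadjusted. On the natural calendar reading, Day 1 is short for every child and a false Day 1 to Day 2 rise follows for most plausible speeds of recovery: 2- to 6-fold at a constant rate, and 1.5- to 4.5-fold where the truth is a 25% fall. These sizes rest on the assumed dose times and an even spread of stools. The direction needs only that treatment begins at noon or later and that the rate does not fall very fast.

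The reach is limited to descriptive stool-count tables. A reader might infer that the primary result is compromised; it is not, because duration of diarrhea is measured in hours from the start of treatment. This is a worthwhile, inexpensive improvement and not a threat to the main conclusion.

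**What to change.** In SAP 9.2.4 and 9.2.5:

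- Count stools and watery stools in consecutive 24-hour periods (0 to 24 h, 24 to 48 h, and so on) from the clock time of the first dose. The diary already records the date and time of every stool and every dose (Protocol 8.3).
- Show the hours observed in each period. Flag incomplete final periods and summarise them apart from complete ones. Do not scale short fragments to 24 hours, because the end of recording depends on recovery.
- State the 12-hour length of the baseline count wherever it appears beside these counts.

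Cost: a few lines of SAP text and minor programming, with no new data. The drawback is that last periods will be incomplete. Under the assumed times, a child treated to 08:00 on day 6 has 116 h (noon start), 110 h (18:00) or 108 h (20:00), that is, four complete periods (96 h) and a fifth of 20, 14 or 12 h. Calendar-day counts can stay in the listing.

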9.2.5 Number of Stools and Watery Stools (Additional Table Requested by Abbott)

Number of stools as well as number of watery stools from start of treatment and until end of study treatment and for each day of the study will be summarized as Table 14.2.5 using FA and PP samples.

Subgroup analysis of number of stools as well as number of watery stools by age group (< 24 months old and \geq 24 months old) will be also summarized as Table 14.2.10 using FA and PP samples.

10.EXTENT OF EXPOSURE AND DRUG COMPLIANCE

The randomization (only for Protocol Version dated 09 OCT 2017) will be listed in Listing 16.2.5.1.

All study drug dispensation and retrieve to each subject will be listed in Listing 16.2.5.2. Individual subject study drug administration record will be listed in Listing 16.2.5.2. In listing 16.2.5.2, for data collection of Racecadotril dosage, a NTF (Abbott_RACE3002_NTF_Racecadotril dosage per sachet_20190321) from Abbott is adapted to extract the dosage with unit from column of "Relevant Information Related to Study Drug Dispensation".

10.1 Extent of Exposure

The way of computing the extent of exposure is listed as below,

The extent of exposure = The date of completion/ termination of the study treatment drug intake - The date of the first study treatment drug intake) + 1]

Number of sachets scheduled to be taken during that treatment period is the collected data from diary card before the last dose (last dose was defined the first dose of the next day after recovery). The extent of exposure for the treatment group will be summarized as Table 14.1.3 using Safety, FA and PP Samples.

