7.1 Treatments to Be Administered

Racecadotril Infants Granules for Oral Suspension 10 mg
Racecadotril Children Granules for Oral Suspension 30 mg

1.5 mg/kg of Racecadotril will be administered, 3 times daily (morning, noon, evening), via the oral route.

In infants less than 9 kg: one 10 mg sachet 3 times daily.
In infants from 9 kg to <13 kg: two 10 mg sachets 3 times daily.
In children from 13 kg to 27 kg: one 30 mg sachet 3 times daily.
In children of more than 27 kg: two 30 mg sachets 3 times daily.

Standard treatment for pediatric subjects with diarrhea is oral rehydration solution (ORS). ORS will be given according to the registered local label of the brand and the instruction of the investigator. At the start of the trial, alignment will be reached on the understanding of treatment of standard ORS with the principal investigator with the aim to use the same brand of ORS and the same age-appropriate standardized treatment pattern for the subjects throughout the trial. ORS treatment will be documented in the CRF. Reporting obligations for ORS by the investigator will follow local regulations for marketed products. Racecadotril will be given in addition to ORS.

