7.8 Treatment Compliance

Drug Accountability

The Investigator is accountable for all clinical drug supplies shipped to his/her study site for the duration of the study. A final accounting of the clinical drug supplies will be required at the completion/termination of the study. The Investigator is required to provide written explanation for any discrepancies.

All used and unused clinical drug supplies will be inventoried and returned to the Sponsor (or an authorized representative) by a designated monitor.

Compliance

Each intake of study drug (Racecadotril) will be recorded in a patient diary and evaluated.

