8 STUDY ASSESSMENTS AND FLOW CHART

8.1 Efficacy Measurements

Primary Efficacy Variable:

Duration of diarrhea (hours) between the start of treatment until the last watery/diarrheal stool before recovery or the end of study treatment (treatment duration maximal 5 days). Treatment will stop at recovery or after the morning dose of day 6, if not recovered.

Duration of diarrhea is defined as date and time of the evacuation of the final watery/diarrheal stool before recovery derived from the daily diary.

Secondary Efficacy Variables:

- Time until recovery, defined as date and time of the evacuation of the first of two consecutive normal stools or no stool within 12 hours after the first normal stool.
- Number of recovered subjects in total and until each individual treatment day.
- Global Physician Assessment (GPA) at the end of treatment, at the discretion of the investigator:
 - 1 = Complete relief of acute diarrhea,
 - 2 = marked improvement of acute diarrhea,
 - 3 = moderate improvement of acute diarrhea,
 - 4 = slight improvement of acute diarrhea,
 - 5 = no change in acute diarrhea,
 - 6 = worsening of acute diarrhea.(Treatment success = GPA score of 1 or 2).
- For toilet trained children only: number of stools per day as well as number of watery stools per day from start of treatment and until end of study treatment.

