8.3 Other Assessments

Informed Consent

Voluntary written informed consent must be obtained from one parent/legal representative prior to performing any study-related procedures (see Section 1.3).

Demographic Data

Demographic data (gender, age, year and month of birth, race) will be collected for all subjects.

Medical History

Any clinical event, including diagnosis, condition, or surgery, that occurred prior to allocation to treatment, is to be recorded on the Medical History form. In case a clinical event concerns a chronic disorder, which means it started in the past and it is still present at the screening visit, it should also be recorded on the Medical History Form. Examples of these events are diabetes, migraine, and hay fever.

Concomitant Medication

All medication taken by the subject during the study (from signing the informed consent form through post-study follow-up) is to be recorded on the Concomitant Medication form, except for study drug.

Subject Diary

The parent(s)/caregiver(s)/legal representative(s) have to document date and time of each individual stool of the subject and the stool consistency (watery, normal) of each evacuation continuously. The subject individual stool consistency before start of the diarrhea is defined as normal (e.g. taking into account the age and diet, e.g. breast feeding, of the individual subject).

Recording can be stopped after the excretion of two consecutive normal stools or no stool within 12 hours.

The date, time and dose of study drug intake as well as the amount ORS consumed has to be recorded.

Fever will be measured twice daily, once in the morning and once in the evening with at least 12-hour interval using the same device and method (preferably ear temperature), by the parent(s)/caregiver(s)/legal representative(s) and documented in the diary including method, time and value.

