10.2 Drug Compliance

The way of computing the drug compliance is listed as below,

The study drug compliance = Number of sachets a subject takes during the treatment period / Number of sachets scheduled to be taken during that treatment period)*100%

The drug compliance for the treatment group will be summarized as Table 14.1.3 using Safety, FA and PP samples as well.

11.SAFETY ANALYSIS

The safety sample will be used for the analysis of the safety and tolerability data.

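### SAP 10.1 takes scheduled sachets from diary data that the protocol describes only as intakes, so the compliance figure may not register missed doses

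*SAP*

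**What the plan says.** SAP 10.2 expresses compliance as a percentage. The numerator is "Number of sachets a subject takes during the treatment period" and the denominator is the number scheduled over that same period. The section does not say where the numerator comes from. SAP 10.1 gives the source of the denominator: "Number of sachets scheduled to be taken during that treatment period is the collected data from diary card before the last dose". It adds that, for a child who recovers, the last dose is the first one on the following day. The result goes into Table 14.1.3 for the Safety, FA and PP samples.

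Protocol 7.8, under Compliance, says: "Each intake of study drug (Racecadotril) will be recorded in a patient diary and evaluated". Protocol 8.3, under Subject Diary, says: "The date, time and dose of study drug intake as well as the amount ORS consumed has to be recorded". Protocol 4.1 likewise lists study drug intake among the diary items. The diary also holds stools, ORS and temperature, but for study drug none of these sections mentions planned or missed doses.

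Protocol 7.8 has a second possible source for sachets taken: "All used and unused clinical drug supplies will be inventoried and returned to the Sponsor". SAP section 10 lists drug dispensed and retrieved in Listing 16.2.5.2 but does not link it to the compliance formula.

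**The concern.** A compliance ratio needs a denominator that does not depend on what the child took. SAP 10.1 does not build it from the three-times-daily regimen and the weight band. It equates the scheduled number with data collected on the diary card, and for study drug the protocol describes those data as intakes. A missed dose would then drop out of the numerator and the denominator together, and the ratio could not fall.

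At stake is whether Table 14.1.3 tells the reader anything about adherence. A value at or near 100% would look reassuring about exposure in a single-arm study while following from the definition alone.

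**Working it through.** The documents state no compliance figure, so there is nothing to reproduce. The check counts dose times from the protocol regimen and applies the SAP 10.2 ratio under each reading of the denominator.

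**Inputs from the documents**
- Three doses a day: morning, noon and evening (Protocol 7.1).
- First dose at noon or in the evening of Day 1 (Protocol 4.1).
- For a recovered child, the last dose falls on the next day (SAP 10.1).
- Without recovery, the last dose is on the morning of Day 6 (Protocol 4.1).

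**Inputs assumed for illustration**
- Recovery on Day 3, with all three Day 3 doses scheduled.
- Two earlier doses missed.
- No planned-dose slots on the diary card.

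**Main example: noon start, last dose in neither term**
1. Dose times scheduled before the last dose: D = 2 (Day 1) + 3 (Day 2) + 3 (Day 3) = 8.
2. Doses taken: D − 2 = 6.
3. Diary-based ratio: (D − 2)/(D − 2) = 6/6 = 100%.
4. Regimen-based ratio: (D − 2)/D = 6/8 = 75.0%.

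The number of sachets per dose cancels when each dose taken is complete.

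**Same example under other choices**
- Noon start, last dose in both terms: diary 7/7 = 100%; regimen 7/9 = 77.8%.
- Evening start, D = 1 + 3 + 3 = 7, last dose in neither term: diary 5/5 = 100%; regimen 5/7 = 71.4%.
- Evening start, last dose in both terms: diary 6/6 = 100%; regimen 6/8 = 75.0%.

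**No recovery, noon start, three doses missed (assumed), Day 6 morning dose taken**
- Dose times: 2 + 4 × 3 + 1 = 15, of which 12 are taken.
- Last dose in both terms: diary 12/12 = 100%; regimen 12/15 = 80.0%.

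**Incomplete doses.** Protocol 7.1 includes a two-sachet band: "In infants from 9 kg to <13 kg: two 10 mg sachets 3 times daily". Suppose a child in that band is given one sachet at each of the 8 dose times. The diary-based ratio is 8/8 = 100%, and the regimen-based ratio is 8/(2 × 8) = 50%.

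**Numerator from returned sachets.** In the main example, with one sachet per dose, dispensed minus returned would also come to 6 if the records agree. The ratio is again 6/6 = 100%. Any departure from 100% would show disagreement between the inventory and the diary, not missed doses.

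**The case against.** The strongest objection is that the defect depends on a form that is not in the documents. The protocol says what caregivers must record, not how the card is laid out. A card with pre-printed dose slots would supply a true scheduled count, and missed doses would then lower the ratio. The SAP may also have meant the diary only to fix the treatment window. SAP 10.2 does distinguish taken from scheduled sachets, which suggests that its authors did not intend the two to be identical. The numerator source is open too: Visit 2 has both a compliance check and collection of study drug, so returned sachets could be used.

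Much of this stands, and it makes the finding conditional. It does not remove it. Neither slots nor a window-only use of the diary is written anywhere, and SAP 10.1 says that the scheduled number is the diary data. A returned-sachet numerator removes the identity of the two terms but still leaves intake in the denominator.

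Two stronger readings are tempting, and the documents do not support them.

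- A reader might infer that compliance will exceed 100%, for example 9/8 = 112.5% with full intake and the last dose counted in the numerator only. That requires the cut before the last dose to apply to the denominator alone, whereas SAP 10.2 ties both terms to the same treatment period.
- A reader might infer that the documents flatly contradict each other on the last dose. Protocol 8.1 and SAP 3.5 do say: "Treatment will stop at recovery or after the morning dose of day 6, if not recovered". But the protocol synopsis puts stopping at recovery and a last dose the next morning in one statement, and Protocol 4.1 and SAP 10.1 also place a last dose after recovery. The short statements may be abbreviations. They still need to be aligned, because they bear on which doses count as scheduled.

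**Conclusion.** The point holds as a minor defect in a definition. As written, and unless the card has planned-dose slots, the denominator in SAP 10.1 counts doses taken. With a diary-based numerator over the same window, which Protocol 7.8 makes the natural reading, compliance is 100% whatever was missed. With a returned-sachet numerator, it does not measure adherence to the schedule.

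In the main example the gap is 100% against 75.0%. That size rests on the assumed start time, recovery day, Day 3 doses and two missed doses. The documents give no expected rate of missed doses, so the effect on the summary as a whole cannot be estimated.

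A reader might also infer that the per-protocol sample or the efficacy results are at risk. They are not: no compliance threshold defines the PP sample, and no efficacy or safety estimate uses the ratio. Individual administration records are listed in Listing 16.2.5.2. Only the descriptive compliance figure in Table 14.1.3 is affected.

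**What to change.** In SAP 10.1 and 10.2:

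- Derive scheduled sachets from the protocol regimen as written: dose times from the first dose to the end of the subject's treatment, multiplied by the sachets per dose for the weight band in Protocol 7.1. For children who do not recover, refer to the Day 6 end point in SAP 3.5. For withdrawn children, refer to the termination date of drug intake already used in SAP 10.1.
- Name the numerator source.
- Use one window for both terms, with the last dose in both or in neither.
- If the card does carry planned-dose slots, say so and define scheduled sachets from them.

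The statements in Protocol 8.1 and SAP 3.5 that treatment stops at recovery should be reconciled with those in the synopsis, Protocol 4.1 and SAP 10.1 that place a last dose on the following morning or day. Which rule applies is for the sponsor to state.

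The cost is SAP wording and one derivation. Intake times and doses, body weight and returned supplies are already collected. One limit is that the diary may end before the last dose, since Protocol 8.3 allows: "Recording can be stopped after the excretion of two consecutive normal stools or no stool within 12 hours". If the last dose is counted, it may have to be taken from returned sachets. The downside is that reported compliance may be lower where doses were missed. With matched windows and full intake it stays at 100%.
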